## 6.2 Data Security

A code will be assigned to every participant and the collected data will be recorded using the participant's unique code for identification purposes. The Principal Investigator, Study Physician and research staff/students who schedule appointments will be the only ones with access to the master code identifier. Participants' hard copy files will be kept in locked cabinets only accessible by authorized research personnel in a secured building. Electronic files will be password-protected and stored on the university's secure server and will only be accessible to authorized research personnel. The master code identifier and the data files will be kept in two separate locations. All personnel who will have access to data of any form will be required to complete CITI training and will only have access to the data during a specific duration deemed necessary by the Principal Investigator.

## 6.3 Data and Safety Monitoring

### A. Periodic Data Evaluation

There will be a local Data and Safety Monitoring Committee composed of 3 Rutgers University faculty and staff members who are not directly involved with the study. The Committee will approve the protocol before the study is initiated, monitor study progress, and ensure that participant safety is addressed adequately. The Committee will receive monthly email updates on study progress and will meet at least once every 2 months. Additional meetings may be called if deemed necessary. Following each meeting, the Committee will provide written documentation regarding findings for the study as a whole and any relevant recommendations related to continuing, modifying or terminating the study. All recommendations will be submitted to the Principal Investigator. A copy of the recommendation will be provided to the Rutgers University IRB. A chairperson will be appointed to provide documentation on behalf of the Committee.

### B. Type of Data Evaluated

The Committee will monitor recruitment, retention, adherence, and review participant safety including adverse events, proposed major protocol modifications, and reports of related studies as appropriate.

**C. Collection of Safety Information**

Safety information will be collected by research personnel at study visits or reported by the participants over the phone.

**D. Frequency Of Data Collection**

Safety data collection will start at the beginning of the first food testing visit and repeat after each study visit. However participants may contact members of the research team to report any potential adverse events anytime during the study.

**E. Reviewer of Data**

Members of the Data and Safety Monitoring Committee will review the data.

**F. Schedule Of Review Of Cumulative Data**

The Committee will receive monthly email updates on study progress and will meet at least once every 2 months. Additional meetings may be called if deemed necessary.

**G. Tests for Safety Data**

Pearson Chi-square tests (two-tailed) will be used to compare the safety data (e.g. number of reported adverse events) after consuming the control food (white bread) and each of the test food to determine whether the dietary fiber supplementation is causing harm comparing to an everyday food item.

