#### **1.3 Research Design and Methods**

**OVERVIEW.** This is a pilot study to characterize the effect of food supplemented with dietary fiber on glycemic response in human. Participants will test 6 food items (plus a control food for comparison) with postprandial glycemic response monitored using a continuous glucose monitoring system. The study will be conducted at the Cook-Douglass Student Health Center and Harvest Café at New Jersey Institute for Food, Nutrition & Health (IFNH). There will be an eligibility screening and group assignment visit, and 14 food testing visits over 4 weeks (Figure 1).

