**GROUP ASSIGNMENT.** Upon confirmation of eligibility, the Research Officer will measure fasting blood glucose concentration (FBG) by performing a finger prick test (ACCU-CHEK® Aviva Plus, Roche Diabetes Care, Indianapolis, IN). Participants who are clinically diagnosed with impaired glucose tolerance or type 2 diabetes (diet-controlled and/or on oral hypoglycemic medications) will be assigned to the Prediabetes/Diabetes group irrespective of their finger prick test results. For participants who are not diagnosed with diabetes, those with FBG < 100 mg/dL will be assigned to the Non-Diabetes group, and those with FBG ≥ 100 mg/dL will be assigned to the Prediabetes/Diabetes group based on classification guidelines from the American Diabetes Association (5). Participants will also be asked to sign up for one of the testing panels: 1) Panel A will test one control food (white bread) and six fiber-supplemented food (dietary fiber mix in water, hot waffle, room temperature waffle, hot pancake, room temperature pancake and muffin); or 2) Panel B will test one control food (white bread) and six fiber-supplemented food (dietary fiber mix in water, sponge cake, crispbread, vegetable smoothie, fruit smoothie and muffin). Finally, the Research Officer will collect information to complete the participant profile, including anthropometry measurements (height and weight), and demographics and contact details.

The eligibility screening and group assignment visit will take approximately 1 h to complete.

**FOOD TESTING.** In the morning of each testing day, participants will attend IFNH between 8 and 10 am after an overnight fast of at least 8 h. They will be required to consume all the study food provided under supervision. The

amount of white bread to be consumed will contain 50 g of available carbohydrates (3-4 slices of bread), and the amount of fiber-supplemented food to be consumed will contain 60 g of dietary fiber mix (approximately 2 waffles, 2 pancakes, 2 slices of sponge cake, 2 serves of crispbread, 2 muffins or 300 ml of smoothies). Participants may leave the research facility after consuming the food, and they will be instructed to refrain from eating and drinking (except water) for the next 3 h. Each food will be tested twice over two consecutive days, with all testing to be completed in 4 weeks (Figure 1). Each food testing session will take approximately 30 min to complete.

[figure not shown]

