#### **4.9 Risks to Subjects**

##### **A. Description of Subject Risk**

The finger prick test and the use of CGM sensor both involve piercing of the skin which may cause infection. However infection is rare.

Participants may experience gastrointestinal symptoms (e.g. bloating, flatulence, diarrhea, constipation or cramping) when they consume the fiber-supplemented test food. These discomforts are common, however, these discomforts are minor and they should not last longer than a few hours.

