**6.0 Research Data Protection and Reporting**

**6.1 Data Management and Confidentiality**

**A. Data analysis plan:** Statistical analyses will be performed using the SPSS Statistics Software Package. Analysis of variance with Tukey's post-hoc test (two-tailed) will be used for intra-and inter-group comparisons of postprandial blood glucose concentration (area-under-curve). Independent-samples *t* test (two-tailed) will be used to analyze variations in other participant characteristics. Statistical significance will be accepted at *p* value < 0.05.

**B. Quality control:** All research personnel will complete CITI training and be knowledgeable about Good Clinical Practice (GCP), relevant regulations and policies. The Principal Investigator will ensure adherence to the study protocol, regulatory requirements, GCP standards at all times. Team meeting will be held on a regular basis to review adherence to study protocol, and to discuss any incidents of failures of protocol compliance, keeping adequate and accurate records, and reporting of adverse events.

**C. Data handling:** The study data will include two key components: 1) a master code identifier that contains the personal information of the participants and the participant code assigned to them; and 2) study data files that contain all the de-identified data generated in this trial. Participants' hard copy files will be kept in locked cabinets only accessible by authorized research personnel in a secured building. Electronic files will be password-protected and stored on the university's secure server and will only be accessible to authorized research personnel. The master code identifier and the data files will be kept in two separate locations. The master code identifier is only accessible to the Principal Investigator, Study Physician and research staff who schedule appointments and the study data files are accessible to authorized research personnel who work in relevant components of the trial. Data in hard copies and the master code identifier will be kept for 6 years after study completion, thereafter they will be shredded. As data will then exist in de-identified form, the electronic data files will be kept indefinitely. The Principal Investigator will be responsible should receipt and/or transmission of data is required. All data transported/shared will be de-identified.

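### The safety test in Section 6.3 G is an unpaired Pearson chi-square on within-person data with no stated unit, so its p-values cannot be relied on at 0.05

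*Combined protocol and SAP*

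**What the plan says.** Section 6.3 G states that "Pearson Chi-square tests (two-tailed) will be used to compare the safety data (e.g. number of reported adverse events) after consuming the control food" and after each test food. The stated purpose is "to determine whether the dietary fiber supplementation is causing harm comparing to an everyday food item". The section gives no significance level of its own; the only one in the protocol is 0.05, in Section 6.1 A.

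Section 1.3 sets a within-person design. In the overview: "Participants will test 6 food items (plus a control food for comparison"). Under group assignment: "Panel A will test one control food (white bread) and six fiber-supplemented food", and Panel B is built the same way. Under food testing: "Each food will be tested twice over two consecutive days". Section 4.5 C requires 20 completers, 10 per panel.

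On data collection, Section 6.3 D says: "Safety data collection will start at the beginning of the first food testing visit and repeat after each study visit". Section 4.9 A warns: "Participants may experience gastrointestinal symptoms (e.g. bloating, flatulence, diarrhea, constipation or cramping) when they consume the fiber-supplemented test food".

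The only other comparison of foods is the analysis of variance in Section 6.1 A, which "will be used for intra-and inter-group comparisons of postprandial blood glucose concentration (area-under-curve"). It covers glucose, not adverse events.

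**The concern.** Pearson's chi-square compares independent groups. Bread and test-food results here come from the same people, and each person contributes two sessions per food. The protocol names no paired or clustered method for safety data.

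The unit is also undefined. A number of events is offered only as an example, safety data are gathered at every visit, and one session can produce several symptoms. An analyst could count people with any event, sessions with any event, or events, and each choice gives the test a different error rate.

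At stake is a question the plan says it will settle: whether the fiber foods cause harm. Two analysts following Section 6.3 G could reach opposite conclusions from the same records. A test that is too conservative would tend to miss harm; one that is too liberal would raise false alarms. Section 6.3 G also does not say how a non-significant result will be reported.

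**Working it through.** The plan gives no event rate, power or sample size for this test, so there is no figure of its own to reproduce.

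**Inputs from the documents**
- Sessions per person: 7 foods × 2 = 14, which agrees with the 14 visits in Section 1.3.
- Completers: 5 × 2 groups × 2 panels = 20, so 10 per panel (Section 4.5 C).
- Distinct test foods: 6 + 6 − 2 shared (fiber mix in water, muffin) = 10. Eight are in one panel only, so the usual comparison has n = 10. It is n = 20 only if the panels are pooled for a shared food.
- Nominal level 0.05 (Section 6.1 A).

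**Assumptions** (the documents give none of these): 30% event rate on bread and food alike; within-person correlation 0, 0.3 or 0.6; mean symptoms per affected session 1 to 2.

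**Why the error moves.** Pearson uses the variance for independent data. The ratio of the true variance of the bread–food difference to that variance is approximately:
- person unit: 1 − r;
- session unit, two sessions per food: 1 + r_within − 2·r_between.

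The large-sample error is then P(|Z| > 1.96/√ratio). For the person unit with r = 0.3 the ratio is 0.7 and the error 0.019; with r = 0.6 the ratio is 0.4 and the error 0.002. For the session unit with r_within = 0.3 and r_between = 0 the ratio is 1.3 and the error 0.086; with both at 0.3 the ratio is 0.7 and the error 0.019.

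**Small-sample results** (uncorrected Pearson; person unit by full enumeration of paired tables, the others by simulation):

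| Unit | Condition | n = 10 | n = 20 |
|---|---|---|---|
| Person | r = 0 / 0.3 / 0.6 | 0.037 / 0.014 / 0.002 | 0.053 / 0.021 / 0.003 |
| Session | independent | 0.053 | 0.048 |
| Session | r = 0.3 across all sessions | 0.023 | 0.020 |
| Session | r = 0.3 within a food only | 0.091 | 0.085 |

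For the event unit the plan gives no formula, so I took (A − B)²/(A + B) on the event totals A and B, with symptoms per affected session distributed as 1 + Binomial(4, (mean − 1)/4). At n = 10:

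| Mean symptoms per affected session | r = 0 | r = 0.3 | r = 0.6 |
|---|---|---|---|
| 1 | 0.017 | 0.007 | 0.002 |
| 1.2 | 0.047 | 0.024 | 0.008 |
| 1.5 | 0.093 | 0.057 | 0.024 |
| 2 | 0.151 | 0.101 | 0.052 |

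At a 15% rate and n = 10 the session figures are 0.049, 0.020 and 0.084, and the event figures span 0.003 to 0.18.

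**Worked example.** Of 10 people, 1 has an event on bread and 6 on a test food.
- Person-level Pearson: 20 × (1×4 − 6×9)² / (10×10×7×13) = 5.49, p = 0.019.
- Same pattern in both sessions, counted by session (2/20 v 12/20): 40 × (2×8 − 12×18)² / (20×20×14×26) = 10.99, p = 0.0009.
- Exact McNemar, if the person who reacted to bread also reacted to the food (5 discordant pairs, all one way): 2 × 0.5⁵ = 0.0625.

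**What n = 10 can show.** If nobody has an event on either food, the 95% Tango interval for the paired difference is −28 to +28 percentage points (−16 to +16 at n = 20). A non-significant result cannot establish absence of harm.

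**The case against.** The strongest reply has four parts.

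1. With the person as unit and non-negative correlation, the error never exceeds 0.053 in these calculations and falls as correlation rises. The fault there is lost sensitivity, not false alarms. That is right, but the plan does not say that the person is the unit.
2. Session-level inflation requires r_within to exceed twice r_between, and the 0.091 sets r_between to zero. With r_within at 0.3, the error is 0.091, 0.067, 0.054, 0.043 and 0.022 as r_between goes through 0, 0.1, 0.15, 0.2 and 0.3. The condition is real, and 0.091 is the end of that range, not a typical value.
3. The event-level figures rest on an assumed statistic and symptom distribution. They illustrate how far the error can move; they do not estimate it for this trial.
4. The wide interval at n = 10 comes from the sample size, which Section 1.5 openly leaves without a power calculation, and a better test does not cure it. This also stands. What can be changed is how a non-significant result is read.

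None of this makes an unpaired test suitable for paired data or supplies the missing unit.

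**Conclusion.** The concern holds. Section 6.3 G names a test that does not match the design in Section 1.3, and nothing elsewhere repairs it or fixes the unit. At n = 10 and an assumed 30% rate, the true size at nominal 0.05 ranges from 0.002 to 0.151 over the units and conditions examined. It can fall below, near or above the nominal level, so this should not be read simply as inflated false positives. The mismatch and the open unit follow from the protocol text alone; the sizes depend on assumed rates, correlations and symptom counts.

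The change should be made, but the consequences are limited. This is a 20-completer pilot, and neither the committee's safety review (Sections 6.3 A, B and E) nor the suspension rule (Section 6.3 H) depends on this test.

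**What to change.** Replace the Pearson test in Section 6.3 G with three sentences:

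> For each food, the safety outcome is whether the participant reported any adverse event after either of its two sessions. Each test food will be compared with white bread by the paired risk difference and its 95% Tango score interval. An interval that includes zero, or p ≥ 0.05, will not be interpreted as absence of harm.

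A Newcombe paired interval would also serve; name one in advance. A mid-p McNemar test may be added as secondary, with a statement that the interval prevails if they disagree. They do disagree at four discordant pairs all in one direction: at n = 10 the Tango interval is +1 to +69 points, while mid-p is 0.0625. Symptom counts can be listed descriptively. It would also help to say how a missed session or a withdrawal before both foods is handled, a gap that the present test has too.

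**Cost.** No new data. Chance of detecting an assumed 10% v 40%, at correlation 0 and 0.3:

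| Method | n = 10 | n = 20 |
|---|---|---|
| Pearson | 0.29, 0.25 | 0.62, 0.64 |
| Tango interval excludes zero | 0.32, 0.35 | 0.57, 0.77 |
| Mid-p McNemar | 0.18, 0.16 | 0.56, 0.69 |
| Exact McNemar | 0.08, 0.06 | 0.43, 0.54 |

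McNemar loses power at n = 10, which is why the interval should be the main result. In this case the interval gives up a little only at n = 20 with zero correlation; small losses also occur under some other alternatives. Over the scenarios examined (null rates of 10% to 50% with correlation up to 0.6, and 10% v 40% with correlation 0 and 0.3), its coverage was at least 94.6%, and with no true difference it wrongly excluded zero with probability at most 0.053.

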### 1.5 Sample Size Justification

No power calculation is performed for this pilot study. We aim to have 5 completers in the Non-Diabetes and 5 in the Prediabetes/Diabetes group, for each of the test panel (i.e. a total of 20 completers). This sample size is comparable to those used in published pilot studies on bran products. Steinert et al (7) used 10 participants (healthy, overweight and obese) to examine the effect of oat bran on glycemic response; Sheflin et al (8) used 7 participants (3 in control and 4 in experimental group) to examine the effect of heat-stabilized rice bran on gut microbiota and metabolites.

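### Section 6.3 G asks one safety question about fiber supplementation but tests it food by food, with no pooled comparison, so equal risks may get conflicting verdicts

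*Combined protocol and SAP*

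**What the plan says.** Section 6.3 G gives the method: "Pearson Chi-square tests (two-tailed) will be used to compare the safety data (e.g. number of reported adverse events") after white bread and after "each of the test food to determine whether the dietary fiber supplementation is causing harm comparing to an everyday food item". It does not say whether the unit is the serving, the participant or the event, or whether a food eaten in one panel is compared with bread from that panel or from both. The only significance level in the protocol is in section 6.1 A: "Statistical significance will be accepted at *p* value < 0.05". I read it as applying to 6.3 G, which sets none of its own.

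Section 1.5 plans "5 completers in the Non-Diabetes and 5 in the Prediabetes/Diabetes group, for each of the test panel (i.e. a total of 20 completers") and adds "No power calculation is performed for this pilot study". Section 1.3 lists six fiber foods per panel, each tested twice. Two of them (mix in water, muffin) are in both panels. On the amount of fiber it says "the amount of fiber-supplemented food to be consumed will contain 60 g of dietary fiber mix".

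Section 4.9 A says of gastrointestinal symptoms: "These discomforts are common, however, these discomforts are minor and they should not last longer than a few hours". It attaches no rate.

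**The concern.** The stated conclusion is a single yes or no about supplementation. The stated evidence is a list of up to 10 p-values, and nothing says how the list becomes the answer. If three foods reach significance and seven do not, 6.3 G does not say whether supplementation has been found harmful.

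Splitting also discards information. Each completer contributes 12 fiber sessions and 2 bread sessions, but a food-level test uses only 2 of the 12. Eight of the 10 foods are eaten by 10 completers each. With so few people per test, foods carrying an identical risk can fall on either side of 0.05 by chance. In the other direction, up to 10 unadjusted tests can produce a flag when there is no excess risk. The Pearson test also treats the same people's repeated servings as independent observations.

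At stake is the tolerability finding that this food-development pilot passes on to the planned study in type 2 diabetes.

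**Working it through.** **Counts from the documents.** Completers: 5 × 2 groups × 2 panels = 20, which reproduces section 1.5. Distinct fiber foods: 6 + 6 − 2 shared = 10. Sessions per completer: 6 × 2 = 12 fiber and 1 × 2 = 2 bread. Eight foods have 10 people (20 servings). Bread, mix in water and muffin have 20 people (40 servings).

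**What one food-level test needs.** For the uncorrected Pearson test, z = (a/n₁ − b/n₂) / √[p(1−p)(1/n₁ + 1/n₂)], with p the pooled proportion.

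- By person, bread from the same panel: 4/10 v 0/10 gives 0.4/√(0.2 × 0.8 × 0.2) = 2.24, p = 0.025. For 3/10 v 0/10, p = 0.060.
- By person, bread from both panels: 2/10 v 0/20 gives 0.2/√(0.0667 × 0.9333 × 0.15) = 2.07, p = 0.038.
- By serving, bread from both panels: 2/20 v 0/40, p = 0.042.

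The minimum number of events is therefore four or two, depending on choices the plan leaves open.

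**Power of one food-level test** (exact enumeration, independent units, assumed risk per unit):

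| Bread v fiber | 10 food v 10 bread | 10 food v 20 bread | 20 food v 40 bread |
|---|---|---|---|
| 5% v 20% | 7% | 28% | 43% |
| 10% v 30% | 14% | 27% | 48% |

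**All 10 foods together.** Simulation: 2,000 trials per scenario, 20 completers, 2 servings per food, the same true risk in every fiber food, and a participant effect with SD 1 on the logit scale. A food counts as flagged if its risk is higher than bread and two-sided p < 0.05. Ranges cover analysis by serving or by participant, with bread pooled over panels or taken within panel. The last column is one pooled test that permutes food labels within participant, at 0.025 in the harm direction. All risks are assumptions.

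| Bread v fiber | Mean foods flagged | 1 to 9 flagged | Pooled test positive |
|---|---|---|---|
| 5% v 5% | 0.06-0.33 | 5-16% | 0.1-0.2% |
| 5% v 15% | 1.2-2.9 | 57-75% | about 35% |
| 5% v 20% | 2.4-4.6 | 80-89% | 70-71% |
| 10% v 30% | 2.9-5.1 | 84-92% | 81-84% |
| 5% v 30% | 5.2-7.7 | 75-94% | 98% |
| 5% v 40% | 7.3-9.3 | 39-84% | over 99% |
| 5% v 60% | 9.6-10.0 | 1-25% | 100% |

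In the 5% v 5% row no trial flagged all ten foods, so the third column is also the chance of at least one false flag. A separate run of the by-serving analysis with pooled bread gave 17%. For orientation, 10 independent tests at 0.05 would give 1 − 0.95¹⁰ = 40% in either direction. The simulated figure is lower because it counts harm only, the tests share bread data and people, and events are few.

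**The case against.** **Food-level results have a use.** This is food development, and section 1.2 describes two mixes, one insoluble and one soluble. Section 1.3 fixes the 60 g amount but does not say which mix goes into which food. It is tempting to say that different verdicts for the same mix must be wrong. The documents do not establish one common mix, and tolerability could differ by mix or food. This stands: it calls for a display by mix and for keeping food-level results, but it does not supply the missing overall answer.

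**The planned tests may raise a signal more often.** In the simulation at least one food is flagged in 80-92% of trials at 5% v 20%, against 70-71% for the pooled test. This also stands. The pooled test buys a single verdict and a controlled false-alarm rate (below 1%, against 5-17%), not more chances of some flag.

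**Stronger readings that the documents do not support.** A reader might infer that most foods will be declared harmless. That depends on rates the protocol does not give, and from about 5% v 30% upward half or more are flagged. A reader might infer that only reported events count. In 6.3 G they are an example, and 6.3 C says "Safety information will be collected by research personnel at study visits or reported by the participants over the phone". A reader might infer that sensor data are ignored for safety, but section 1.3 has the Research Physician review them. Nor does the protocol say that a non-significant test clears a food.

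**Consequences are bounded.** Neither the Committee's review nor the suspension rule in 6.3 H is tied to these tests. This stands, and it makes the point an inexpensive improvement, not a safety failure.

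**Conclusion.** The point holds in this form. Section 6.3 G poses one question and plans no analysis that answers it, whatever the event rates. Under equal assumed risks of 5% v 20% or 10% v 30%, conflicting food-level verdicts may arise in about 80-92% of trials. With no excess risk, at least one food is flagged in roughly 5-17%. These figures rest on assumed rates, a participant SD of 1, equal risk in all fiber foods and 20 completers. They vary with the unit of analysis and the bread data used. At high fiber risks the conflict largely disappears, because nearly every food is flagged.

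**What to change.** Make the main 6.3 G analysis one within-participant comparison of event risk per session, all fiber sessions against bread sessions, by an exact test stratified by participant or by conditional logistic regression. Report the risk difference with a 95% CI. State which mix each food contains and, if the foods use different mixes, show the comparison by mix as well. Report each food descriptively, with counts and CIs.

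Optionally, tabulate event severity and the sensor data already under physician review beside it. These are additions, and the point does not depend on them.

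The main change costs SAP wording and no new data. The downsides are that food-specific harm claims become descriptive, and that the pooled exact test is conservative when events are sparse: power is about 35% at 5% v 15%. A non-significant pooled result should therefore be read through its confidence interval, not as evidence of no harm.

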**C. Require Number of Subjects to Complete Research**

20 (5 each in Panel A Non-Diabetes group and Prediabetes/Diabetes group, same two groups for Panel B)

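### Section 6.3 G addresses harm with a chi-square test and no effect estimate or interval; with about 10 people per food, p ≥ 0.05 cannot support a conclusion of no harm

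*Combined protocol and SAP*

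**What the plan says.** Section 6.3 G states: "Pearson Chi-square tests (two-tailed) will be used to compare the safety data (e.g. number of reported adverse events", with white bread set against each test food. The purpose given is "to determine whether the dietary fiber supplementation is causing harm comparing to an everyday food item". The section names no effect measure, confidence interval, tolerable excess risk or unit of analysis.

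The only significance threshold in the document is in Section 6.1 A: "Statistical significance will be accepted at *p* value < 0.05". It is not repeated in 6.3 G.

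On size, Section 1.5 says "No power calculation is performed for this pilot study", and Section 4.5 C requires "20 (5 each in Panel A Non-Diabetes group and Prediabetes/Diabetes group, same two groups for Panel B". In Section 1.3, white bread, the fiber mix in water and the muffin appear in both panels and the other foods in one. "Each food will be tested twice over two consecutive days".

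Section 4.9 A expects gastrointestinal symptoms after the fiber foods and says of them: "These discomforts are common, however, these discomforts are minor and they should not last longer than a few hours". It gives no rate.

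**The concern.** A test whose declared job is to answer whether the fiber causes harm invites a yes-or-no answer. With about 10 people per food, a large excess of symptoms can easily give p ≥ 0.05, and the plan provides no other number that would show how large an excess remains compatible with the data.

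This matters because the pilot supplies information for developing a dietary intervention in type 2 diabetes (Sections 1.1 A and 1.2). Tolerability of each food is part of what the later study needs. A list of p-values does not convey it, and a null result worded as no harm would sit badly beside Section 4.9 A. Changing to a paired test would not remove the problem, because a non-significant paired p-value from 10 to 20 people does not show absence of harm either.

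**Working it through.** The documents give no safety event rate, margin or power figure, so there is no stated figure to reproduce.

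**Inputs.** From the documents: 5 + 5 = 10 completers per panel (4.5 C); 2 × 10 = 20 for foods in both panels (1.3); each food eaten twice (1.3), so six test foods give 12 fiber servings against 2 of bread; threshold 0.05 (6.1 A), assumed to apply to 6.3 G as well. Assumed: the person-level event risks used in step 2.

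**1. What the stated test does with small counts.** For a 2×2 table with cells a, b, c, d, uncorrected Pearson χ² = N(ad − bc)² / (product of the four margins).

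| Food v bread | Calculation | χ² | p |
|---|---|---|---|
| 3/10 v 0/10 | 20 × 30² / (10·10·3·17) | 3.53 | 0.060 |
| 4/10 v 0/10 | 20 × 40² / (10·10·4·16) | 5.00 | 0.025 |
| 5/10 v 1/10 | 20 × 40² / (10·10·6·14) | 3.81 | 0.051 |
| 3/10 v 0/20 (bread from both panels) | 30 × 60² / (10·20·3·27) | 6.67 | 0.0098 |
| 6/20 v 0/20 (sessions) | 40 × 120² / (20·20·6·34) | 7.06 | 0.008 |
| 3/20 v 0/20 (sessions) | 40 × 60² / (20·20·3·37) | 3.24 | 0.072 |

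The first and fourth rows have the same number ill on the food and none on bread, yet fall on opposite sides of 0.05. Section 6.3 G does not say which count applies. The same people eat both foods; with three discordant pairs, all in one direction, exact McNemar gives p = 2 × 0.5³ = 0.25.

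**2. Chance of missing a real excess.** I enumerated every pair of binomial counts and summed the probability of p < 0.05 in the harmful direction. One minus that sum is the miss rate. Counts on the two foods are treated as independent, as the stated test does.

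| Assumed risk, bread v food | 10 v 10 | Food 10 v bread 20 | 20 v 20 |
|---|---|---|---|
| 5% v 20% | 93% | 72% | 71% |
| 5% v 30% | 77% | 53% | 41% |
| 10% v 30% | 86% | 73% | 64% |
| 10% v 50% | 53% | 32% | 16% |

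**3. What an interval would show.**
- For 3/10 v 0/10 the difference is 0.30. The Wilson limits are 0.108 to 0.603 for 3/10 and 0 to 0.278 for 0/10. Newcombe's paired interval, with correlation 0 because nobody has an event on bread, has lower limit 0.30 − √(0.192² + 0.278²) = −0.04 and upper limit 0.30 + (0.603 − 0.30) = 0.60.
- For 0/10 v 0/10 the same method gives an upper limit of 0.28.
- For 0/10 on a single food, the one-sided 95% exact upper limit on the risk is 1 − 0.05^(1/10) = 0.26.

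**4. Combining the fiber foods.** Any event over 12 fiber servings cannot be set directly against any event over 2 bread servings. With an equal, independent 5% risk per serving (assumed), the two proportions would be 1 − 0.95¹² = 46% and 1 − 0.95² = 10%, with no true difference.

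**The case against.** The strongest case on the other side is that several tempting readings go further than the text.

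- **That p ≥ 0.05 will be read as not harmful.** A reader might infer this from the purpose stated in 6.3 G, but the plan gives no rule for a null result. It could equally mean only that harm was not shown.
- **That a food making 3 of 10 people ill would pass.** This holds only for one count per person against the same panel's 10 bread eaters. Against bread from both panels, or with 6/20 v 0/20 sessions, the same test flags harm.
- **That a p-value is the whole safety assessment.** It is the only quantitative element of 6.3 G, but an independent committee also reviews adverse events and can recommend modifying or terminating the study (6.3 A, B and E). Three ill participants of ten would be visible to it. The committee has no numerical criterion, however, and the suspension rule in 6.3 H covers only life-threatening or fatal related events.
- **That the test selects foods for the next study.** Sections 1.1 A and 1.2 say the pilot informs development; nothing makes the 6.3 G result a go/no-go rule.

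It is also fair that low power is expected in a pilot that openly did no power calculation, that the risks in step 2 are assumed, and that an interval does not enlarge what 10 people can show.

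All of this stands, and it limits the point. It does not supply an effect estimate, or settle the unit, the denominator or the reading of a null result. Miss rates remain high with 20 bread eaters for all but the largest assumed excess.

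**Conclusion.** The point holds in a limited form. Section 6.3 G gives a test, and nothing else quantitative, as the means of deciding whether the fiber causes harm, and it leaves open how a non-significant result will be read. With 10 to 20 people per food, p ≥ 0.05 cannot support a conclusion of no harm. A rise from 10% to 30% would be missed about 86% of the time at 10 v 10 and about 73% at 10 v 20, and even 0 v 0 events in 10 people leaves an excess of about 28 points within the 95% interval.

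The miss rates rest on assumed person-level risks, on independent counts and on the 0.05 threshold carrying over from 6.1 A. The conclusion about null results does not depend on the particular risks chosen. The documents do not show that the sponsor intends to declare foods safe on this test; the gap is that nothing in the plan prevents it.

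**What to change.** In Section 6.3 G:

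1. Define the unit as the participant, with any event on that food scored yes or no over its two servings.
2. As the main safety result for each test food, report the within-person risk difference (test food minus white bread) with a paired 95% confidence interval, using the same participants for both foods.
3. Report the same for all fiber foods together, allowing for the larger number of servings. One way is to average each participant's six food-level indicators and subtract the bread indicator, so that every indicator rests on two servings. The interval is then taken over participants.
4. State that p ≥ 0.05 will not be reported as absence of harm.

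No tolerable excess is given in the documents, so the interval should be reported as an estimate and not turned into a pass/fail rule. The cost is a few sentences and one interval per comparison, with no new data, visits or participants. The downside is that the intervals will be wide, and the report will not be able to claim no harm for any food.
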